7.3.1. Continuous Endpoints

The continuous endpoints include:

- Hemoglobin
- Bilirubin (total)

The above endpoints will be summarized by visit, starting at Baseline/Day 0 and will continue through the Week 77 visit. Summary tables will include change from baseline and individual summary statistics will follow those presented in [Section 5.2.1](#). For patients with more than 12 months of follow-up in Part B, all endpoints at the Week 79 visit and beyond will be provided in a data listing.

Line plots of mean hemoglobin and bilirubin over time, starting at Baseline/Day 0, will be presented. Additionally, a line plot of mean change from baseline in hemoglobin over time, starting at Baseline/Day 0, will be presented.

Additionally, the following continuous endpoints will be summarized by Study Period using FAS as specified in [Section 5.2.1](#):

- Number of transfusions and total transfusion units
- Annualized number of transfusions and annualized transfusion units

For number of transfusions and total transfusion units, data up to Week 77 will be considered, for both Part B and Combined Study Period summaries. All data after Week 77 will be provided in the listing.

For annualized number of transfusions and annualized transfusion units, all Part B data will be considered. Annualized values will be calculated for each patient using the following formula:

$$\text{Annualized value} = \frac{\text{Number of events during the Study Period}}{\text{Total number of days during the Study Period}} \times 365.25$$

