4.4 DURATION OF THE STUDY

The planned total study duration per patient is approximately 2.5 to 3.5 years:

- Screening/Observation Period: 6 weeks (Day -42 through Day -1)
- Part A treatment period: 25 weeks (Day 0 through Day 175)
- Part A EOT visit: 1 week after administration of the last dose of study drug during Part A (Week 26/Day 182)

Patients who complete study Part A per protocol through the EOT visit will participate in Part B, the long-term safety and durability of response extension phase of the study.

- Part B safety and durability of response extension phase: bi-weekly dosing starting at Week 27 visit. For individual patients, dosing in Part B may last from 2 to 3 years, depending on when the patient enters Part B. Part B will run for 2 years following completion of LPO in Part A.

- Part A/B ET/Safety Follow-up visit: 9 weeks after administration of the last dose of study drug.

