3.5. Interim Analysis

For the purposes of regulatory submission, an interim analysis of safety and efficacy data will be performed for Part B after all patients have completed Part A, while Part B is still ongoing. Additional interim analyses of Part B data may be performed to obtain interim safety and efficacy results at the Sponsor's discretion for purposes of regulatory filings and requests, publications, or future planning. In general, these analyses will include safety and efficacy endpoints indicated in [Section 2.2.1](#) and [Section 2.2.2](#) through certain cutoff dates.

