4.1. Full Analysis Set (FAS)

The Full Analysis Set is defined as all subjects who enroll into the Part B study and receive at least 1 dose (including partial dose) of study drug. The Full Analysis Set is synonymous with the Intent-to-Treat Population described in the protocol.

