5.1.1. Definitions

Study Day

Study Day is defined as days relative to the date of first dose of BIVV009 in Part A, Day 0. The start/stop day of events will be calculated as (date of event – date of Day 0 +1).

Incomplete dates will be imputed for the calculation of study days, unless specified otherwise:

- If missing day only, the start date will be imputed as the first day of the month, while the end date will be imputed as the last day of the month;
- If missing day and month, the start date will be imputed as the first day of the year, while the end date will be imputed as the last day of the year;

Baseline

Baseline is defined as the last non-missing value prior to the first administration of study drug in Part A. If a transfusion occurred during the screening period, the baseline measure must be at least 7 days after the transfusion.

Study Treatment Period

For subjects who enroll into Part B, the Part A study treatment period starts at the date of first study drug administration and ends at the date of Week 26 visit. The Part B study treatment period starts following completion of Part A (ie, immediately following Week 26 visit) and ends at the ET/EOS/Safety follow-up visit, which is 9 weeks after each subjects' last dose.

The Combined Study Period includes all visits in Part A and Part B and will be utilized for a subset of analyses in order to support regulatory submissions and/or publications.

Visit Windows

Analysis by study visit will utilize the data recorded on the corresponding nominal visit from electronic Case Report Forms (eCRFs). In case of missing data/assessments for a visit, data from an unscheduled visit, or ET/Safety Follow-up Visit will be used, if the Study Day of such a

visit fits in the analytic window defined below. If multiple values are identified within the analytic window, the one closest to the target study day will be used.

- Starting at Week 27 and every 2 weeks thereafter, analytic visit windows in Part B will be -6 days to +7 days from the Target Study Days of the protocol-defined visits. An example of the first few visits in Part B can be seen in Table 1, below.

Table 1: Analytic Visit Windows

Visit	Target Study Day	Analytic Visit Window (Study Day)
Week 27	189	183-196
Week 29	203	197-210
Week 31	217	211-224
Week 33	231	225-238
Etc.		

Solicited Symptomatic Anemia

Refer to the Part A SAP for definitions regarding the severity of CAD symptomatic anemia.

Thromboembolic Events

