5.2. Data Summaries

5.2.1. Continuous Variables

Continuous variables will be summarized using descriptive statistics including the number of non-missing values (n), mean, standard deviation (SD), median, minimum, and maximum.

Where specified in the table shells, the 25th and 75th percentiles will also be provided. Means, medians, and the 25th and 75th percentiles will be presented to one decimal place beyond that with which the data were captured. SDs will be presented to two decimal places beyond that with which the data were captured. Minimum and maximum will be displayed to the same number of decimal places as that with which the data were captured.

Unless impractical within a given table, statistics will be aligned by the decimal place (or assumed decimal place) in the summary tables.

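### The mean Part B annualised transfusion rate gives every patient equal weight whatever the follow-up, so it is unstable at an early interim cut; a pooled rate per patient-year should be the main figure

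*SAP*

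**What the plan says.** Part B SAP Section 7.3.1 lists the annualised number of transfusions and the annualised units as continuous endpoints, summarised by study period. "Annualized values will be calculated for each patient using the following formula": events in the period, divided by that patient's days in the period, times 365.25. On the data used, "For annualized number of transfusions and annualized transfusion units, all Part B data will be considered".

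The summary follows Section 5.2.1: "Continuous variables will be summarized using descriptive statistics including the number of non-missing values (n), mean, standard deviation (SD), median, minimum, and maximum". No weighting by follow-up, minimum follow-up, pooled rate or confidence interval is given.

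Three other passages settle how short the follow-up can be:

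- **Population.** Section 4.1 takes "all subjects who enroll into the Part B study and receive at least 1 dose (including partial dose) of study drug".
- **End of period.** Section 5.1.1 starts Part B straight after the Week 26 visit. The period "ends at the ET/EOS/Safety follow-up visit, which is 9 weeks after each" subject's last dose. It gives no end for a patient still on treatment at a data cut.
- **Interim.** Section 3.5 plans an analysis that "will be performed for Part B after all patients have completed Part A, while Part B is still ongoing". In general it covers the efficacy endpoints of Section 2.2.2, which include transfusion requirements, up to cutoff dates that are not fixed.

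**The concern.** A rate from a few days of observation is either zero or very large. Averaging it with equal weight alongside rates from a year or more lets one event in one briefly observed patient move the mean a long way.

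This matters because durability of response is the secondary objective of Part B and transfusion requirement is one of its endpoints. The annualised value is also the only transfusion summary adjusted for exposure, and the only one that counts repeat transfusions over all Part B data. The raw counts stop at Week 77 and ignore differences in follow-up. The Kaplan-Meier analysis uses only the first transfusion and starts its clock in Part A.

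The interim is meant for regulatory submission, so an unstable mean would be read outside the study team. Section 5.1.3 of the Part B SAP recognises that treatment duration varies, but responds only by limiting by-visit efficacy summaries to 12 months.

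**Working it through.** The documents give no planned figure for this endpoint, so there is none to reproduce. The check applies the SAP formula to stated scenarios.

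**Inputs from the documents**
- Per-patient formula and unweighted summary: Part B SAP 7.3.1 and 5.2.1.
- About 20 patients enrolled: Protocol 7.10.
- Part B entry spread over about 1 year: Protocol 4.4 gives 2 to 3 years of Part B dosing, depending on entry date.
- Length of Part B: 1 year after the last patient leaves Part A in the Part B SAP, 2 years in the current protocol. Both are run.
- First Part B dose: "bi-weekly dosing starting at Week 27 visit" (Protocol 4.4), about 7 days after Part B starts.

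**Assumptions not in the documents**
- 20 patients in Part B (15 as an alternative).
- Evenly spaced follow-up times.
- Last entrant 14 days into Part B at the cut (7 and 28 as alternatives).
- True rate of 0.5 to 2 transfusions per year, constant, Poisson.

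**Step 1: one event in a short period.** One transfusion in d days annualises to 365.25/d and adds (365.25/d)/N to the mean.

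| d (days) | Annualised | Added to mean, N = 20 | Added to mean, N = 15 |
|---|---|---|---|
| 7 | 52.2 | 2.61 | 3.48 |
| 14 | 26.1 | 1.30 | 1.74 |
| 28 | 13.0 | 0.65 | 0.87 |
| 70 | 5.2 | 0.26 | 0.35 |

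**Step 2: interim, 20 patients at 14 to 365 days, the other 19 at 1 per year.** Total time is 20 × (14 + 365)/2 = 3,790 days = 10.38 patient-years. The other 19 contribute 3,776/365.25 = 10.34 events.

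- Planned mean without the event: 19 × 1/20 = 0.95. With it: 0.95 + 26.09/20 = 2.25.
- Pooled rate without the event: 10.34/10.38 = 1.00. With it: 11.34/10.38 = 1.09.
- Weight of the 14-day patient: 1/20 = 5% in the mean, 14/3,790 = 0.4% in the pooled rate.
- Share of the planned mean due to that one event: 1.30/2.25 = 58%. With the others at 0.5 or 2 per year it is 73% or 41%.

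**Step 3: variance.** With rate λ and follow-up t in years, Var(mean of rates) = λΣ(1/t)/N² and Var(pooled rate) = λ/Σt. The ratio is Σ(1/t) × Σt/N², which does not depend on λ.

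| Scenario (N = 20) | Σ(1/t) | Σt | Ratio |
|---|---|---|---|
| Interim, shortest 14 days | 80.56 | 10.38 | 2.1 |
| Final, one leaver at 70 days, others 2 to 3 years | 12.94 | 47.66 | 1.5 |
| Final, one leaver at 70 days, others 1 to 2 years | 18.46 | 28.67 | 1.3 |
| Final, no early leaver, 2 to 3 years | 8.13 | 49.97 | 1.02 |
| Combined period at the interim, shortest 182 + 14 = 196 days | 21.57 | 20.34 | 1.1 |

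The interim ratio is 2.9 if the shortest follow-up is 7 days and 1.6 if it is 28 days.

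**Step 4: why 70 days at the final analysis.** A patient who takes one Part B dose and attends the follow-up visit has 7 + 63 = 70 days. One transfusion in that time moves the planned mean from 0.95 to 0.95 + 5.22/20 = 1.21, with the others at 1 per year.

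**The case against.** The strongest case against has five parts.

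- **It is one descriptive summary among several.** Part B tests no hypothesis and names no single durability result. The median, minimum and maximum are reported with the mean, as are raw counts and units to Week 77, Kaplan-Meier time to first transfusion, and haemoglobin and other markers. None of these is distorted in this way. A reader might infer that one patient can dominate the Part B durability result, but the documents do not support that. The median is a weak substitute, though: it is zero if most patients need no transfusion.
- **The 9-week rule limits short follow-up at the final analysis.** Follow-up of only days then needs death or loss before that visit. This stands, and it makes the final-analysis effect moderate or negligible.
- **Very short follow-up at the interim is not certain.** No cutoff date is fixed, and Section 3.5 does not say that the cut falls as the last patient leaves Part A. Even with 14 days of follow-up, the chance of any transfusion is 1 − exp(−λ × 14/365.25), which is 2% to 7% at 0.5 to 2 per year. This stands: the exposure is plausible and its consequence large, but it may not occur.
- **The planned mean is not biased in itself.** With a constant rate and follow-up unrelated to outcome, it is unbiased and only imprecise. Upward bias needs early leaving to be linked to transfusion, and that direction would be unfavourable to the drug.
- **Pooling targets a different quantity.** It estimates events per patient-year, not the average patient's rate, and gives early leavers little weight. This stands and argues for showing both.

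**Conclusion.** The point holds for one summary: the mean Part B annualised rate of transfusions and of units. Equal weighting with no minimum follow-up makes that mean unstable when some patients have been observed briefly.

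The effect is material at an early interim cut. The variance ratio is about 2.1, and one event in a 14-day patient supplies 41% to 73% of the mean. With one early leaver at about 70 days the final-analysis ratio is 1.3 to 1.5. With none it is 1.02 when patients are followed for 2 to 3 years. In the Combined Study Period at the interim it is about 1.1.

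These figures rest on 20 Part B patients, evenly spread entry, a constant Poisson rate and a cut 14 days after the last entry. The documents fix none of these.

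The change is worth making because this is the only exposure-adjusted transfusion summary. The sponsor already divides total events by total subject-time, with an exact CI, for thromboembolic events in Part A (Part A SAP 7.4.1.2.2). Protocol 7.4.2 also provides for 95% CIs in Part B where appropriate, and Section 5.2.1 of the Part B SAP supplies none.

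**What to change.** Amend Part B SAP Section 7.3.1 as follows:

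1. For each study period, report total transfusions divided by total patient-years, and total units divided by total patient-years, as the main rates.
2. Give each a 95% CI that allows for between-patient variation. A patient-level bootstrap is practical with about 20 patients; another method with that property would also do. Name a fallback for a period with no transfusions, where a bootstrap gives no usable interval.
3. For patients still on treatment at a data cut, count events and follow-up to the cutoff date.
4. Keep the per-patient annualised median and range as supportive summaries beside the pooled rate.

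The cost is SAP wording and one extra table, from data already collected. The pooled rate gives little weight to patients who leave early; showing the per-patient values beside it keeps that visible.

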7.3.2. Time-to-event Endpoints

The time-to-event endpoints include:

- Time to first transfusion (after the first 5 weeks of study drug administration in Part A)

The above endpoint will be summarized using FAS as specified in [Section 5.2.3](#). All data, including those beyond the Week 77 visit, will be utilized for calculating the above, time-to-event endpoints. However, summary tables and figures will only present data up to and including Day 539 (ie, Study Day 540, target study day for the Week 77 visit). All other data after Study Day 540 will be provided in a listing.

8. SAFETY ANALYSIS

Unless stated otherwise, all safety data will be summarized for subjects in the Safety Analysis Set defined in [Section 4.2](#). The summary tables may also be presented by subgroup based on the BIVV009 dose cohort. However, the limited number of subjects in each dose cohort and non-randomized assignment preclude a direct comparison between the two dose cohorts.

8.1. Adverse Events

AEs will be classified using the MedDRA system organ classes and preferred terms. MedDRA version 20.1 or higher will be used throughout the study. In general, AEs will be analyzed based on *incidence*, defined as the proportion of subjects who had at least one occurrence of an event out of the number of subjects in the Safety Analysis Set.

All summary tables and listings will only include treatment-emergent adverse events in Part B unless noted otherwise. An AE will be regarded as treatment-emergent for Part B if the date of AE onset is on or after the Part B start date. If an AE started in Part A but worsened in Part B, a new record will be created in Part B and be treated as a TEAE in Part B.

Unless specified otherwise, system organ classes and preferred terms within each SOC will be presented alphabetically. For the purpose of summarization, a subject is counted once in a SOC or preferred term if the subject reported one or more events in that SOC or preferred term. Unless specified otherwise, percentages will be based on the number of subjects in the Safety Analysis Set.

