2. STUDY OBJECTIVES AND ENDPOINTS

2.1. Study Objectives

2.1.1. Primary Objective

The primary objective of Part B is to evaluate the long-term safety and tolerability of BIVV009 in patients with CAD.

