5.1.3. Handling of Missing Data

Best efforts will be utilized to minimize missing values. If a subject discontinues study treatment early, the subject will be asked to complete study assessments at ET/safety follow up visit.

For the analysis of both continuous and categorical data, summary statistics will be computed based on observed data. Since the duration of treatment period varies in Part B, efficacy endpoints by visit will be summarized through 12 months during Part B. Additional summaries beyond 12 months may be computed depending on the enrollment pattern, i.e., the number of subjects attending visits after the Week 77 visit. AE endpoints by visit will be summarized through LPLV in Part B.

For a QOL endpoint, in the event of missing data, the total score will be estimated according to the provision for missing domains in the calculation algorithm of the score. For example, if a subject has missing data in FACIT-F questionnaire at a visit, the prorated FACIT-F score will be calculated if more than 50% of the items (a minimum of 7 out of 13 items) are available. Otherwise, the score is missing.

For the analysis of AEs and concomitant medications/procedures, if the start/stop date of an AE/concomitant medication/procedure is missing or partial, the corresponding study day will be left blank. However, inferences will be made from the partial and missing dates to classify medications as prior and/or concomitant and AEs as treatment emergent or not treatment emergent. These inferences are described in [Section 8.1](#).

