6.5.1. Exposure

Study drug exposure, measured by the duration of study treatment, the number of BIVV009 administrations and total actual BIVV009 dose, will be summarized by study period for the Safety Analysis Set.

The duration of the study treatment (in weeks) is calculated as follows:

1. Combined Study Period: $(\text{date of last dose} - \text{date of first dose in Part A} + 15)/7$
2. Part B Study Period: $(\text{date of last dose} - \text{Part B start date} + 15)/7$

The actual dose administered at each visit is calculated as:

$$\text{Total volume administered} / \text{Total volume prepared} * \text{assigned dose.}$$

The total BIVV009 dose will be summarized as follows:

1. Combined Study Period: The summation of all actual doses administered in Parts A and B.
2. Part B Study Period: The summation of all actual doses administered in Part B, alone.

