8.1.1. Overall Summary of Adverse Events

An overall summary of TEAEs will be provided which tabulates the number and percentage of subjects who experienced a TEAE, related TEAE, treatment-emergent SAE, treatment-emergent related SAE, treatment-emergent Grade 3 or higher AE, treatment-emergent infections of Grade 3 or higher severity, TEAE thromboembolic event, and TEAEs within 24 hours after the start of infusion; the number and percentage of subjects who discontinued treatment and/or the study due to an AE; and the number and percentage of subjects who died. In addition, the number of TEAEs, TESAEs, TEAE thromboembolic events and TEAEs within 24 hours after the start of infusion will be presented.

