8.1.6. Adverse Events of Interest

8.1.6.1. AEs within 24 Hours after the Start of Infusion

All AEs within 24 hours after the start of infusion are captured in the eCRF. Incidence of AEs within 24 hours after the start of infusion will be summarized by SOC and preferred term.

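### Part B's primary objective is long-term safety, but the plan gives no adverse event rate per unit of time although follow-up is long and unequal

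*SAP*

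**What the plan says.** **Objective.** Part B SAP 2.1.1: "The primary objective of Part B is to evaluate the long-term safety and tolerability of BIVV009 in patients with CAD".

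**Measure.** Part B SAP 8.1 summarises AEs by a measure "defined as the proportion of subjects who had at least one occurrence of an event out of the number of subjects" dosed in Part B, and adds that "percentages will be based on the number of subjects in the Safety Analysis Set". Sections 8.1.1 to 8.1.6 apply this to TEAEs, SAEs, Grade 3 or higher events and infections. For infusion-related events, 8.1.6.1 says: "Incidence of AEs within 24 hours after the start of infusion will be summarized by SOC and preferred term".

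**Counts and exposure.** Section 8.1.1 adds event counts for four categories: "In addition, the number of TEAEs, TESAEs, TEAE thromboembolic events and TEAEs within 24 hours after the start of infusion will be presented". Infections of Grade 3 or higher are not among them. Section 6.5.1 summarises treatment duration, number of administrations and total dose, but does not link them to AEs. The AE tables listed in section 11 contain no rate per patient-year, Kaplan-Meier estimate or fixed-interval summary.

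**Follow-up.** Protocol 4.4 says that "dosing in Part B may last from 2 to 3 years, depending on when the patient enters Part B". The Part B SAP (1, 3.1, 3.1.2, 3.1.3) still has Part B ending 1 year after the last patient leaves Part A. Its section 5.1.3 begins "Since the duration of treatment period varies in Part B" and, for that reason, limits by-visit efficacy summaries to 12 months, while AE summaries run to the last patient's last visit. Section 3.5 plans an interim analysis of Part B while it is ongoing, with further cuts at the sponsor's discretion.

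**Time-based measures elsewhere.** Part A SAP 7.4.1.2.2 analyses thromboembolic events after Week 5 per subject-year with an exact 95% CI. Part B SAP 7.3.1 annualises transfusions by days in the Study Period. Part B SAP 7.2.2, with 5.2.2, treats thromboembolic events as a categorical endpoint, that is, as counts and percentages.

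**The concern.** The proportion of patients with at least one event rises with follow-up even when the underlying risk is flat. When follow-up is long and differs between patients, a single proportion mixes risk with time observed. It cannot show whether risk rises, falls or stays level as treatment continues, which is a natural question for a long-term safety objective.

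At an interim cut the proportion also pools patients who have only just entered Part B with patients followed for much longer. For thromboembolic events the two parts use different scales, so their results cannot be set side by side without reworking one of them.

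**Working it through.** **Figure in the plan.** There is none to reproduce: Part B SAP 3.3 states that no sample size or power analysis was done for Part B.

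**Inputs.** Part A follow-up is 26 weeks, or 26/52.18 = 0.498 years. Part B follow-up is at least 1 year by the Part B SAP and 2 to 3 years by protocol 4.4. These are about 2.0, 4.0 and 6.0 times Part A (1, 2 and 3 divided by 0.498). The documents give no AE rate, so the 26-week proportion p is an assumption, shown over a range.

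**Formulas.** With a constant rate of first events, λ = −ln(1 − p)/0.498 per patient-year, and the proportion with an event by T years is 1 − exp(−λT). For p = 20%, λ = 0.2231/0.498 = 0.448, and at 2 years 1 − exp(−0.896) = 59%.

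| Assumed proportion at 26 weeks | λ per patient-year | 1 year | 2 years | 3 years |
|---|---|---|---|---|
| 5% | 0.10 | 10% | 19% | 27% |
| 10% | 0.21 | 19% | 35% | 47% |
| 20% | 0.45 | 36% | 59% | 74% |
| 30% | 0.72 | 51% | 76% | 88% |
| 50% | 1.39 | 75% | 94% | 99% |

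Each row has one unchanged risk. A rate per patient-year would be the same in every column.

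**A fall in risk can be hidden.** If the rate behind the 20% row dropped to a quarter (0.448/4 = 0.112), the 2-year proportion would be 1 − exp(−0.224) = 20%, equal to the 26-week figure.

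**Interim cut.** By the protocol, Part B ends 2 years after the last patient leaves Part A, and a patient may be dosed in Part B for up to 3 years. At a cut made about when that last patient leaves Part A, Part B follow-up therefore runs from about 0 to about 3 − 2 = 1 year. In the 20% row, expected proportions run from near 0% to 36% depending only on entry date.

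**Infusions.** Part A has 14 scheduled doses (Part A SAP 6.5.2). Two-weekly dosing for 2 to 3 years gives about 52 to 78, so a per-patient percentage for 24-hour events also rises with time.

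**Precision of interval rates.** Twenty patients over 6 months give at most 20 × 0.5 = 10 patient-years. At an assumed 0.2 per year, 2 events are expected. The exact 95% limits for 2 events are about 0.24 and 7.2, or about 2 to 72 per 100 patient-years.

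**The case against.** A reader might infer that the Part B result will mostly reflect time on study, or that the objective calls for a comparison with Part A. The documents support neither. The objective names no comparison, every AE table is a Part B table, the study has one arm, and Part B tests no hypothesis (3.2). An apparent several-fold increase arises only if a reader sets the two parts side by side, and its size depends on assumed rates and a constant hazard. It would be smaller for events that cluster early.

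A reader might also infer that crude proportions are the only output. That is too strong. With four overall counts and an exposure summary, a rough overall rate, including one per infusion, is a single division away. Among patients who complete Part B under the protocol the spread is also moderate: 59% against 74% in the 20% row (about 1.25-fold), and 52 against 78 infusions (1.5-fold). Section 5.1.3 does mention AE endpoints by visit, although section 11 lists no such table.

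These points limit the concern but do not remove it. A rate worked out by hand would not be available by organ class, preferred term, grade or relatedness, nor for Grade 3 or higher infections, and would have no planned confidence interval. The interim spread and the two scales for thromboembolic events remain.

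**Conclusion.** The point holds as a gap in reporting the Part B primary objective. It does not bias a planned test. That no person-time AE measure is planned, and that the same plans use such measures for Part A thromboembolic events and Part B transfusions, can be read directly from the documents and needs no assumed rate.

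The size does rest on assumptions. Under a constant rate, 20% over 26 weeks corresponds to about 36% at the SAP's 1-year minimum and 59% to 74% at the protocol's 2 to 3 years; for 5% the figures are about 10%, and 19% to 27%. Which column applies depends on reconciling the Part B duration, since the SAP and the current protocol differ.

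**What to change.** In Part B SAP 8.1 and the section 11 table list:

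- Keep the crude proportions. Add events per 100 patient-years with exact 95% CIs for TEAEs, SAEs, infections of Grade 3 or higher and thromboembolic events, for Part A, Part B and the Combined Study Period.
- Report AEs within 24 hours of infusion per 100 infusions, using the number of administrations from 6.5.1.
- Name the denominator as days in the Study Period, as 7.3.1 does for transfusions. That period runs to the visit 9 weeks after the last dose (5.1.1) and so matches AE collection. Treatment duration in 6.5.1 ends about 2 weeks after the last dose and would leave out time in which events are still counted.
- State the analysis set for the Part A rate, because the Part B Safety Analysis Set omits patients who stopped in Part A.
- Limit any breakdown by interval to total TEAEs. Interval rates for rarer events in about 20 patients would be too imprecise to read.
- Reconcile the Part B duration: 1 year after the last patient leaves Part A in the SAP, 2 years in the protocol.

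The cost is SAP wording and a few table columns from data already collected. Intervals for rare events will be wide. Exact limits treat events as independent, so for AEs that recur within a patient they will tend to be too narrow and should be read as descriptive.
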